Study Title: Robotically Augmented Mental Practice for Neuromotor Facilitation

Document Title: Study Protocol and Statistical Analysis Plan

NCT: NCT04962698

Document Date: 08/25/2023

Protocol

This study consists of experiments on two non-consecutive days in the Human Neuromuscular Physiology Laboratory located in the Biological Sciences/Applied Physiology Building of Georgia Tech. If subjects qualify and agree to take part in this study, subjects will be asked to read and sign the consent form. The whole procedure will last about 3 hours per day, including preparation. Subjects will come to the lab on two separate days on the same tasks. The first day will serve as familiarization with the same tasks as the second day. Subjects will perform the following experiment.

Individuals will sit upright and relax their hands and shoulders. The right shoulder will be fixed with pads to the upper arm to prevent shoulder flexion/extension movement. The right hand and forearm will be rested on a plate hidden below a table. The robotic prosthesis will be placed on the table as one would normally place own arm on the table. There will be no physical connection between the hand and the robotic prosthesis.

Subjects will activate a pair of the front portion of the shoulder muscles and the upper part of the chest muscles for making a grasping movement of the robotic prosthesis. For making a releasing movement of the prosthesis, subjects will activate a pair of the back portion of the shoulder muscles and the back muscles. Muscle activity will be recorded with two small sensors on each muscle. Subjects will practice activation of each muscle pair while watching the signal on a monitor. In each pair, a clearer signal will be used for controlling the robotic digits.

Healthy subjects (N = 18):

Healthy subjects will perform the following tasks A-F. [A: Rest] Subjects will relax their muscles without physical or cognitive effort while gazing at the turned-off monitor. [B: Robotic action observation] Subjects will relax their muscles and focus on observing the computer-controlled grasp and release actions (2 s in each movement) of the robotic hand. [C: Visual MI] Subjects will relax their muscles and perform conventional visual mental imagery (MI). With the guidance of audio instruction, the subjects will imagine the grasp and release motions with the right arm for 2 s in each motion in their mind. There will be no proximal muscle contraction. [D: Kinesthetic MI] The same MI procedure as Task C will be performed, except that the subjects will focus on the kinesthetic sensation that they would feel with the imagined motions. [E: Robotic-Hand Interaction (see below detailed description)] Subjects will perform robotic-hand interaction for grasp and release motions with the activation control of the proximal muscles. During this task, subjects will also imagine the kinesthetic sensation that they would feel with the corresponding motions with the right arm. [F: Virtual-Hand Interaction] Subjects will perform Task E with visual feedback of virtual robot actions in 2D on a monitor. [G: Robotic-Hand Interaction without MI] Subjects will perform Task E without MI. As a reaction task, subjects will flex the index finger as soon as they hear an auditory cue.

Post-stroke subjects (N = 4):

Tasks C [Visual MI], E [Robotic-Hand Interaction], and A [Rest] above will be performed by post-stroke subjects with right-side hemiparesis who can volitionally activate fingers and proximal muscles. As a reaction task, subjects will flex the index finger as soon as they hear an auditory cue. The data on post-stroke subjects will be obtained to test the feasibility of the Robotic-Hand Interaction and observe potential trends. The data will not be used for statistical analysis.

Robot-Hand Interaction with and without MI (Task E and F above):

An individual will use proximal muscle contractions to flex and extend the robotic prosthesis digits for performing a grasp-release task. 1) Grasp. The individual will activate the proximal muscles as if for a retrieving motion (the back portion of the shoulder muscles and the back muscles) for 2 s. This muscle activation controls the prosthesis to flex the digits to grasp a cylinder-shaped object. 2) Release. The individual will relax the above-activated proximal muscles and activate the proximal muscles as if for a reaching motion (the front portion of the shoulder muscles and the top portion of the chest muscles) for 2 s. This muscle activation controls the prosthesis to extend the digits to release the object. After releasing the object, the individual will relax their proximal muscles. The individual will repeat this sequence while observing and hearing the actions of the prosthesis. The acceleration signal will be used to determine the slight displacement of the upper arm. EMG of the forearm and hand muscles will be monitored to ensure that those muscles are relaxed during proximal muscle activation.

TMS test

During the above-mentioned tasks, brain stimulation (called TMS) will be applied over the motor cortex in the left hemisphere. The TMS procedure will follow the one used in our previous studies. A TMS coil will be placed over a precise point on the scalp where we will stimulate the brain to make the muscle move. We will tell the subject when the stimulation portion of the procedure is about to begin. The first part of the procedure will be to find the area of the brain that controls muscles. We will position the TMS coil on the head and will give the subject a series of stimulations (called magnetic pulses). Once we find the spot that controls the muscles, we will find the least amount of stimulation needed to activate the resting muscles. The second part of the procedure will be to evoke muscle contraction with TMS at rest and during the tasks described above. We will apply single-pulse and paired-pulse TMS with 5-second intervals or more. Peak-to-peak amplitude of the motor evoked potential (MEP) will be determined.

Reaction time test

Subjects will be asked to exert finger flexion force with their index finger as soon as they hear an auditory cue for the reaction task. In this test, the focus was on immediacy, and there will be no instruction on the amount of force to produce. The audio cue timing will be randomly varied during the middle 60% during the flexion and extension phases of the artificial or imaginary finger. Reaction time, maximal rate of force development, peak EMG, and peak force will be determined.

Statistical Analysis

Statistical analysis will be performed on data from 18 healthy subjects. The independent variable will be the task. The dependent variables will include MEP amplitude, reaction time, maximal rate for force development, peak EMG, and peak force. If the assumption of sphericity is not violated, the variable will be tested with one-way analysis of variance (ANOVA) with repeated measures on task, followed by a posthoc Bonferroni-corrected pair-wise comparison, when appropriate. If the assumption of sphericity is violated, the variables will be with the Friedman test, followed by the Wilcoxon signed-rank test when appropriate. The alpha value of 0.05 will be used to determine the significance. The alpha value will be corrected for repeated comparisons.

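### Both planned overall tests need a complete row, so one missing task removes a healthy subject from that outcome's overall test, and the plan does not say whether the pairwise tests follow.

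*Combined protocol and SAP*

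**What the plan says.** The analysis population is given in one line: "Statistical analysis will be performed on data from 18 healthy subjects". Task is the only factor ("The independent variable will be the task"), and there are five dependent variables: MEP amplitude, reaction time, maximal rate of force development, peak EMG and peak force.

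Where sphericity holds, the plan is that "the variable will be tested with one-way analysis of variance (ANOVA) with repeated measures on task". Bonferroni-corrected comparisons of task pairs come next. If sphericity is violated, the plan moves to the Friedman test and then the Wilcoxon signed-rank test.

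The number of task levels is ambiguous. The protocol announces "Healthy subjects will perform the following tasks A-F" but then lists a seventh: "G: Robotic-Hand Interaction without MI] Subjects will perform Task E without MI". Both counts are carried below.

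On workload, "The whole procedure will last about 3 hours per day, including preparation". On the two days, "The first day will serve as familiarization with the same tasks as the second day". I read this to mean that Day 2 supplies the analysed data, although the Statistical Analysis section does not say so.

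Nothing in the document covers a task that is stopped or unusable, an incomplete subject, or which subjects enter a pairwise test.

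**The concern.** Every subject has to give a usable value in six or seven tasks, for both a TMS test and a reaction test. Tasks E, F and G depend on driving a prosthesis or virtual hand with proximal muscles. The TMS test section follows a requirement that forearm and hand EMG be monitored for relaxation, with no rule for what happens to a task when relaxation fails. Isolated gaps are therefore plausible.

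Repeated-measures ANOVA and Friedman both work on complete blocks. One gap removes the whole subject from the overall test of that outcome, including values that bear directly on contrasts among the remaining tasks. If gaps fall mostly in the robot-control tasks, the overall test also leans towards subjects who control the device well, even for what it says about rest, observation and imagery. The pairwise step is left open, so its sample size could be settled after the data are seen.

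**Working it through.** **No figure to reproduce.** The document gives N = 18 and alpha 0.05, but no power, effect size, standard deviation or loss rate. Loss rates and effect sizes below are assumptions.

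**1. Do the overall tests need complete rows?** I took simulated data for 18 subjects and 7 tasks and deleted one value. A standard repeated-measures ANOVA routine stopped because the data were unbalanced, and a standard Friedman routine returned no result. Both ran only after that subject was removed (n = 17). A pair not involving the missing task still had 18 subjects; a pair involving it had 17.

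**2. What one gap costs.** With k tasks there are k(k−1)/2 pairs, of which (k−1)(k−2)/2 do not involve the missing task. The ANOVA error df are (k−1)(n−1).

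| | 6 tasks | 7 tasks |
|---|---|---|
| Valid values discarded from the overall test | 5 | 6 |
| Error df, n = 18 to n = 17 | 85 to 80 | 102 to 96 |
| Pairs that can keep n = 18 | 10 of 15 | 15 of 21 |
| Pairs that fall to n = 17 | 5 of 15 | 6 of 21 |

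**3. Overall-test power.** Assume one task is shifted by 1.0 within-subject SD, so the noncentrality is n(1 − 1/k). For k = 7 this is 18 × 6/7 = 15.4 at n = 18 and 17 × 6/7 = 14.6 at n = 17. Power goes from 0.829 to 0.801, or to 0.736 at n = 15. For k = 6 it goes from 0.840 to 0.814, or to 0.750. These compare with no loss at all, so they are an upper bound on what a better analysis could recover.

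**4. Complete rows against available pairs.** Let m be an assumed independent loss rate per task. Expected complete subjects are 18(1−m)^k, and expected subjects per pair are 18(1−m)².

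| m | Complete, 6 tasks | Complete, 7 tasks | Per available pair |
|---|---|---|---|
| 1% | 16.9 | 16.8 | 17.6 |
| 2% | 15.9 | 15.6 | 17.3 |
| 5% | 13.2 | 12.6 | 16.2 |

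At m = 1%, the chance of at least one incomplete row in an outcome is 1 − 0.99^(18k): 66% for six tasks and 72% for seven.

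**5. Pairwise power, if the pairwise tests were also complete-row.** Two-sided paired t test, standardised paired difference 1.0, noncentral t with noncentrality √n, subject counts rounded to whole numbers.

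- Seven tasks, alpha 0.05/21: n = 18 gives 0.734, n = 17 gives 0.688, n = 16 gives 0.636, n = 13 gives 0.456.
- Six tasks, alpha 0.05/15: n = 18 gives 0.778, n = 17 gives 0.735, n = 16 gives 0.688.

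The fair comparison is complete rows against available pairs. For seven tasks at 2% loss that is n = 16 against n = 17, or 64% against 69%. At 5% it is n = 13 against n = 16, or 46% against 64%. The interval half-width, in SDs of the difference, is t/√n: 0.9119 at n = 16 and 0.8740 at n = 17, a ratio of 1.043.

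**6. Clustered loss.** If E, F and G are always lost together at the same average rate, the chance per subject is 7m/3. Complete subjects are then 18(1 − 7m/3) = 17.6, 17.2 and 15.9 at 1%, 2% and 5%. Pairs involving E, F or G have the same n under either rule. With those three tasks lost in two subjects, seven tasks, and an assumed between-task correlation of 0.6, a mixed-model contrast between E and an observed task such as C has a standard error 0.978 times that from the 16 complete rows. A contrast among E, F and G gains nothing.

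**The case against.** **The subject is not shown to be lost from every comparison.** A reader might infer that from the complete-row overall tests. The document does not support it: a Wilcoxon signed-rank test or a paired test needs only the two tasks compared, and nothing says the pairwise step inherits the deletion. The loss is also per outcome; an unusable MEP value does not affect the reaction-time analysis. This objection stands.

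**Nothing invites replacement of subjects or use of Day 1 values.** A reader might infer either from the fixed figure of 18. Neither appears anywhere in the document, which does not even say whether 18 means enrolled or completed. This also stands.

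**A fall in power from 73% to 64%, with an interval 8.5% wider, overstates the case.** Those figures compare n = 16 with n = 18 (0.9119/0.8404 = 1.085), but available-pair analysis does not restore 18 once values are missing. Against what it would deliver at 2% loss, the cost is about 69% to 64%, and 4.3% in width.

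**Loss may be clustered and rare.** Subjects practise with signal feedback, the clearer signal of each muscle pair is used, and a familiarization day comes first. Failures of control would probably hit E, F and G together. Available-pair tests then recover no subjects for the robotic comparisons. That is right for those tests. A mixed model still gains a little, about 2% in standard error under the assumptions above.

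**A mixed model brings assumptions of its own.** A random intercept alone implies compound symmetry, and poor control that itself causes the gap may not be missing at random. Both are fair. The first has to be handled in the fix; the second limits what any available-data analysis can promise.

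**Conclusion.** The concern holds in a limited form. Both planned overall tests drop a subject with one missing task from that outcome's overall test and discard five or six valid values, and the rule for pairwise tests is unstated. A method that keeps those values is available at little cost, so this goes beyond a request for more detail.

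The size is modest: one lost row costs at most about 3 percentage points of overall-test power under the assumed shift. The pairwise figure of roughly 64% against 69% needs three assumptions: 2% independent loss per task over seven tasks, a standardised paired difference of 1.0, and pairwise tests that are complete-row. Clustered loss makes the gain smaller, and with no gaps there is none. The conclusion does not depend on whether there are six or seven tasks. The change should be made, but its absence would not invalidate the study.

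**What to change.** In the Statistical Analysis section:

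- Replace the repeated-measures ANOVA with a linear mixed model for each outcome (task fixed, subject random, Kenward-Roger degrees of freedom), fitted to every available Day 2 subject-task value.
- Where sphericity is violated, replace complete-row Friedman with either the same model under an unstructured or heterogeneous covariance, or a rank test that allows incomplete blocks, such as Skillings-Mack. Name the choice in advance. An unstructured matrix for seven tasks has 7 × 8/2 = 28 parameters, which is a lot for 18 subjects, so the heterogeneous structure or the rank test may be more practical.
- State that each pairwise comparison, including Wilcoxon, uses all subjects with both tasks.
- Describe the population as all healthy subjects with Day 2 data, and report n per task and outcome.
- Give the complete-row analysis as a sensitivity check.
- Reconcile the A to F announcement with the A to G list, since it sets the number of levels and pairs.

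The cost is a few sentences and a standard routine. The downside is the assumption that tasks are missing at random given the observed ones. With complete data the model's task estimates equal the ANOVA's, and Skillings-Mack reduces to Friedman. Choosing the unstructured or heterogeneous model for the second route would change that test even with complete data.

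### Holm's step-down procedure can replace single-step Bonferroni for the task-pair comparisons: same 0.05 familywise bound, never fewer rejections, no added subjects

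*Combined protocol and SAP*

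**What the plan says.** The Statistical Analysis section sets the sample ("Statistical analysis will be performed on data from 18 healthy subjects"), treats task as the within-subject factor and lists five outcomes. If sphericity holds, each outcome gets a one-way repeated-measures ANOVA, "followed by a posthoc Bonferroni-corrected pair-wise comparison, when appropriate". If not, it gets a Friedman test, "followed by the Wilcoxon signed-rank test when appropriate". The level is given as "The alpha value of 0.05 will be used to determine the significance", and the section closes with "The alpha value will be corrected for repeated comparisons". That sentence brings the Wilcoxon tests under correction without naming a method. There is no step-down procedure, restricted set of pairs, simultaneous confidence interval, effect size or power calculation.

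The number of pairs has to be inferred. The healthy-subjects section opens with "Healthy subjects will perform the following tasks A-F", but its list goes on to "G: Robotic-Hand Interaction without MI] Subjects will perform Task E without MI". The later heading "Robot-Hand Interaction with and without MI (Task E and F above" pairs E with F, although F is the virtual-hand task and G is the one without imagery.

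**The concern.** Single-step Bonferroni holds every pair to 0.05 divided by the total number of pairs, however many pairs have already been declared different. Once some pairs are rejected, fewer can still be true nulls, and part of the 0.05 allowance goes unused. Holm uses that part and keeps the same guarantee.

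Power is what is at stake. Each outcome has 15 or 21 comparisons on 18 subjects. Tasks E, F and G are closely related, so more than one real difference from the other tasks is plausible, and that is the situation in which Holm gains most.

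**Working it through.** The plan has no power figure to reproduce.

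**Inputs from the document.** N = 18; familywise level 0.05; k = 7 tasks if G is counted, 6 if only A to F are. **Assumptions.** Two-sided tests; all task pairs compared; d = mean difference divided by the SD of the paired differences; the effect patterns below. The plan does not say whether the ANOVA pairs use their own paired differences or the pooled ANOVA error, so both are shown.

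**1. Thresholds.** Pairs m = k(k−1)/2: 7×6/2 = 21, or 6×5/2 = 15.
- Bonferroni, every pair: 0.05/21 = 0.00238, or 0.05/15 = 0.00333.
- Holm, i-th smallest p against 0.05/(m−i+1): 0.00238, 0.05/20 = 0.00250, 0.05/19 = 0.00263, … 0.05; or 0.00333, 0.05/14 = 0.00357, 0.05/13 = 0.00385, … 0.05.

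**2. Holm never rejects less.** If Bonferroni rejects r pairs, these have the r smallest p values. Each is at most 0.05/m, which is no larger than 0.05/(m−i+1), so Holm passes its first r steps too. In 200,000 random sets of p values for each m, no pair was rejected by Bonferroni and kept by Holm.

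**3. Same familywise bound.** Let m0 be the number of true nulls. When Holm first rejects a true null, at most m−m0 pairs have been rejected before it, so its threshold is at most 0.05/m0. Summed over the m0 true nulls this is at most 0.05, whatever the dependence between pairs that share a task.

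**4. Bonferroni power by noncentral t.** Noncentrality is d√18; at d = 0.8 it is 3.39. Degrees of freedom are 17 (paired), or 17×6 = 102 and 17×5 = 85 (pooled).

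| d | Paired, 21 / 15 pairs | Pooled, 21 / 15 pairs |
|---|---|---|
| 0.6 | 20.4% / 24.1% | 29.1% / 32.5% |
| 0.8 | 46.1% / 51.3% | 61.0% / 64.5% |
| 1.0 | 73.4% / 77.8% | 86.6% / 88.5% |
| 1.2 | 91.1% / 93.2% | 97.4% / 97.9% |

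**5. Power for the A–E pair, Bonferroni to Holm.** Simulation, spherical data, 20,000 trials per scenario, d = 0.8.

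| Pattern | Error term | 7 tasks | 6 tasks |
|---|---|---|---|
| Only E differs | paired | 45.6% → 47.7% | 51.1% → 53.7% |
| Only E differs | pooled | 61.0% → 62.9% | 64.7% → 66.9% |
| F, G (or F) at half effect | paired | 46.2% → 47.9% | 51.2% → 53.5% |
| F, G (or F) at half effect | pooled | 61.6% → 63.1% | 64.7% → 66.6% |
| E, F, G (or E, F) shift equally | paired | 46.8% → 51.8% | 51.0% → 56.1% |
| E, F, G (or E, F) shift equally | pooled | 61.3% → 66.2% | 64.4% → 69.0% |

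Requiring a significant ANOVA first moves these powers by at most 0.3 points. Over d = 0.6 to 1.2 the gain is 0.9 to 6.5 points (paired) and 0.4 to 4.9 (pooled).

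**6. Pairs declared, d = 0.8.** With seven tasks and an equal shift there are 3×4 = 12 true pairs; the number found rises from 5.5 to 6.1 (paired) or 7.3 to 7.9 (pooled). Holm declares at least one extra pair in 42% of trials there, in 29–31% with six tasks and an equal shift, and in 11–12% if only E differs.

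**7. Wilcoxon branch.** Exact p values; two assumed non-spherical covariances (AR(1) with 0.7, and SD doubled for E, F and G); only trials failing Mauchly's test kept. At d = 0.8, Bonferroni power is 43–45% (6 tasks) and 41–43% (7 tasks); Holm adds about 3.0 to 7.5 and 0.4 to 4.7 points. Bonferroni is itself an assumed comparator here.

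**8. Realised familywise error.** Holm's was 1.6–4.3% in the ANOVA-branch settings and at most 3.8% in the Wilcoxon branch. In a separate paired-test run, both methods gave 4.2% when no task differed; with one or two tasks shifted by d = 1, Bonferroni gave 2.1–3.1% and Holm 3.6–3.8%.

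**The case against.** The strongest reply is that nothing is broken. Bonferroni after a repeated-measures ANOVA is standard and valid, every effect size here is assumed, and the gain is small: about 2 points if one task differs, and under half a point in the least favourable Wilcoxon case. All of that is true, and four more points stand.

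- Holm's first step is the Bonferroni test, so the chance of finding any difference does not change. At d = 0.8 with seven tasks (paired error) it was 85.3% under both methods if only E differs, and 97.5% under both with an equal shift.
- The guarantee is the same but the realised error is not. With seven tasks, an equal shift and d = 1.2, it rose from 1.95% to 4.1%, still inside 5%.
- Bonferroni also caps the expected number of false rejections at 0.05, and Holm does not. With six tasks, only E different and d = 1.2, that number rose from 0.035 to 0.053. Bonferroni's simple simultaneous intervals are lost as well. The plan asks for neither property.
- For the Wilcoxon tests no method is named, so the present wording already permits Holm. The gap there is one of specification, not of efficiency.

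The count of 15 or 21 also assumes that every outcome uses every task. The reaction cue is timed to movement phases of a prosthetic or imagined finger, and Rest has neither, so its place in the reaction-time family is not explicit. The lettering conflict is a separate drafting matter, and the case for Holm does not depend on it.

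None of this touches the central comparison: at the plan's own stated level of control, Holm cannot do worse and sometimes does better.

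**Conclusion.** The point holds as an improvement to a valid plan, not as the correction of an error. That Holm rejects at least as much under the same 0.05 bound is algebra and rests on no assumed effect. The size of the gain does rest on assumptions: at N = 18 and d = 0.8 it is about 2 points of power per pair if one task differs and about 5 if two or three shift equally, under either error term. The benefit begins with the second rejected pair. It is modest, but worth taking because it costs nothing that the plan relies on.

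**What to change.** In the Statistical Analysis section, replace the Bonferroni step with wording such as: *all task pairs will be compared, with p values adjusted by Holm's method to a familywise error of 0.05 within each outcome*. Apply the same adjustment to the Wilcoxon signed-rank p values. State which error term the ANOVA-branch pairs use; either is compatible with Holm. Reconcile the A-to-F list and the heading that refers to E and F with the defined Task G, and state which tasks enter each outcome's family, so that the number of pairs is fixed.

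The cost is a few sentences: no extra subjects, measurements or tests. The wording makes explicit two ordinary readings that the plan leaves unstated: that all pairs are compared, and that the family is one outcome. Like the present text, it does not adjust across the five outcomes. The change should be fixed before outcome data are examined.
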